#### **2.4.4.1 Analyses of adverse events**

##### ***Generalities***

Summary tables of each solicited reaction will be presented with number of subjects who reported each solicited reactions occurring within 7 days after the day of injection (D0 to D7). The intensity, the time to onset and number of days of occurrence of each solicited reaction will be summarized. When more than 1 intensity level is reported within a time period, the highest intensity will be used.

Unsolicited AEs will be collected and coded by System Organ Class (SOC) and Preferred Term (PT), using the MedDRA currently in effect at Sanofi at the time of database lock. For each type of unsolicited AE, the number of subjects with at least one instance of that event will be reported. Unsolicited AEs will also be tabulated by relationship to the vaccine group and intensity.

Adverse event incidence tables will present the terms (LLT) prelisted in the CRB for solicited reactions, the SOC and PT for unsolicited AEs, and the number (n) and percentage (%) of subjects experiencing an AE. Multiple occurrences of the same event in the same subject during the study period will be counted only once in the tables.

Sorting within tables ensures the same presentation for the set of all AEs within the observation period. For that purpose, the table of all solicited reactions presented using the terms (LLT) prelisted in the CRB will be sorted by order in the CRB for all similar tables unless otherwise specified. The table of unsolicited AEs presented using primary SOC and PT will be sorted by SOC internationally agreed order and PT sorted by decreasing frequency according to all unsolicited AE summary for all other similar tables unless otherwise specified. In case of equal frequencies of PTs within a SOC, the alphabetic order will be applied.

##### ***Safety overview***

The following AEs within 28 days after vaccination will be summarized.

- Immediate unsolicited systemic AE and AR
- Solicited reaction
- Solicited injection site reaction
- Solicited systemic reaction
- Unsolicited AE and AR
- Unsolicited non-serious AE and AR
- Unsolicited non-serious injection site AR
- Unsolicited non-serious systemic AE and AR

- AE leading to study discontinuation
- SAE
  - Death
- AE of special interest

This safety overview will also be summarized by the following subgroups:

- Age: 65-<75 and  $\geq 75$  years
- Sex: Male and Female
- Previous influenza vaccination status: Yes and No
- Baseline seropositivity status:  $<10$  [1/dil] and  $\geq 10$  [1/dil]

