12.1.1.2 Statistical Methods

Safety

Safety results will be described for subjects in safety analysis set who received QIV-HD IM, QIV-HD SC, or QIV-SD SC. Solicited reactions (solicited injection site and systemic reactions), unsolicited AEs, SAEs, and AESIs will be summarized. The main parameters will be described with 95 % CI based on the Clopper-Pearson method (14).

- Unsolicited systemic AEs occurring within 30 minutes of injection (immediate unsolicited AEs)
- Solicited injection site reactions (pain, erythema, swelling, induration, and bruising) occurring within 7 days after the day of injection (D0 to D7) according to presence, time to onset, number of days of occurrence, maximum intensity (Grade 1, Grade 2, or Grade 3) and action taken. When more than 1 intensity level is reported within a time period, the highest intensity will be used.
- Solicited systemic reactions (fever, headache, malaise, myalgia, and shivering) occurring within 7 days after the day of injection (D0 to D7) according to presence, time to onset, number of days of occurrence, maximum intensity (Grade 1, Grade 2, or Grade 3) and

action taken. When more than 1 intensity level is reported within a time period, the highest intensity will be used.

- Unsolicited AEs occurring within 28 days after the day of injection by system organ class (SOC) and PT, time to onset, duration, maximum intensity (Grade 1, Grade 2, and Grade 3), and relationship to vaccination (for systemic AEs only).
- All SAEs that occur throughout the study by SOC and PT, time to onset, seriousness criteria, outcome and relationship to vaccination.
- All AESIs reported throughout the study by SOC and PT and relationship to vaccination.

Immunogenicity

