## **Blood Sampling**

All subjects will provide a pre-vaccination blood sample at V1 (D0) and a post-vaccination blood sample at V3 (D28 [+ 7 days]).

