### **2.1.4 Safety endpoints**

The endpoints for the evaluation of safety are:

- Occurrence, nature (Medical Dictionary for Regulatory Activities [MedDRA] preferred term [PT]), duration, maximum intensity, and relationship to vaccination of any unsolicited systemic AEs reported in the 30 minutes after vaccination
- Occurrence, time to onset, number of days of occurrence, maximum intensity, action taken, and whether the reaction led to early termination from the study, of solicited (prelisted in the subject's diary card and CRB) injection site reactions and systemic reactions occurring up to 7 days (D0 through D7) after vaccination
- Occurrence, nature (MedDRA PT), time to onset, duration, intensity, relationship to vaccination (for systemic AEs only), and whether the event led to early termination from the study, of unsolicited AEs up to 28 days (D0 through D28) after vaccination
- Occurrence, nature (MedDRA PT), time to onset, seriousness criteria, relationship to vaccination, outcome, and whether the SAE led to early termination from the study, of SAEs throughout the study (D0 through V3)

- Occurrence, nature (MedDRA PT), and relationship to vaccination of AESIs throughout the study (D0 through V3)

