- Whether the AE was related to the investigational product (for unsolicited systemic AEs)
- The Investigator will assess the causal relationship between the AE and the investigational product as either "Not related" or "Related", as described in Section 9.1.3.5 of the protocol.
- Action taken for each event (e.g., medication)

The action(s) taken by the subject to treat and/or manage any unsolicited AEs will be classified in the CRB using the following list (all applicable items should be checked):

- None
- Medication
- Health care provider contact
- Hospitalized
- Whether the AE was serious

For each SAE, the investigator will complete all seriousness criteria that apply (outcome and elapsed time)

- Whether the AE was AESI
- Whether the AE caused study discontinuation

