### ***AEs of Special Interest (AESIs)***

AESIs will be listed by each AESI as shown in [Table 7](#) separately.

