##### **AEs of special interest (AESIs):**

AESIs will be collected throughout the study (D0 through V3). AESIs will have the same detailed information collected as SAEs. Each AESI will be retrieved using the following (as shown in [Table 7](#)):

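### The AESI endpoint runs to V3 (up to D35), but the SAP counts AESIs only within 28 days and omits the whole-study AESI summary planned in the protocol

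*SAP*

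**What the plan says.** SAP 2.1.4, like protocol 9.1.2, defines the AESI endpoint as "Occurrence, nature (MedDRA PT), and relationship to vaccination of AESIs throughout the study (D0 through V3". SAP 1.4 places "a post-vaccination blood sample at V3 (D28 [+ 7 days", so V3 falls between D28 and D35. The PPAS definition in SAP 2.3.2 uses the same 28-to-35-day window.

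Protocol 12.1.1.2 names AESIs among the data to be summarized and specifies the summary: "All AESIs reported throughout the study by SOC and PT and relationship to vaccination".

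In SAP 2.4.4.1, AESIs appear twice. They have a row in the safety overview, where the whole block is introduced by "The following AEs within 28 days after vaccination will be summarized". They also have a short subsection that provides only a listing: "AESIs will be listed by each AESI as shown in" Table 7. SAEs, whose endpoint period is also D0 through V3, get tables both for 28 days and for the whole study.

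On identification, SAP 2.1.4.1.2.3 has the site record for each unsolicited AE "Whether the AE was AESI". SAP 2.5.2.4 then says "Each AESI will be retrieved using the following (as shown in" Table 7, and does not mention the recorded flag.

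SAP 1.6, the place for statistical modifications made in the SAP, is marked as not applicable.

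**The concern.** An endpoint and the table that reports it should cover the same period. Here the endpoint ends at V3 and the only count ends at D28. The same SAP section handles the two periods separately for SAEs, so the distinction was available and was not applied to AESIs.

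The summary planned in the protocol is also missing. The overview row gives occurrence only. Unlike the unsolicited AE rows, it has no companion row for related events, and no AESI table shows SOC, PT or relationship. Two of the three components of the endpoint, nature and relationship, are therefore not tabulated for AESIs as a class, even inside 28 days.

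What is at stake is the reading of a safety category in which one case matters. A report could show zero AESIs in its table and one AESI in its listing, and the table is what is likely to be carried into summaries.

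**Working it through.** The documents state no figure on this point to reproduce. The check sets the output rules side by side, then does two small calculations.

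**Step 1. Where does each kind of AESI appear?** This is traced from SAP 2.4.4.1, 2.5.2.2, 2.5.2.3 and 2.5.2.4.

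| AESI | Onset D0 to D28 | Onset D29 to V3 |
|---|---|---|
| Serious, PT in Table 7 | Overview AESI row; SAE tables; AESI listing | Whole-study SAE tables, not labelled as AESI; AESI listing |
| Non-serious, PT in Table 7 | Overview AESI row; unsolicited AE tables; AESI listing | No table; AESI listing and the separate listing of AEs outside the analysis |
| Flagged by the investigator, PT outside Table 7 | General AE or SAE tables; AESI status not stated | SAE tables if serious, separate listing if not; AESI status not stated |

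The cell with no table follows from SAP 2.5.2.2, which takes non-serious unsolicited AEs with onset after 28 days out of the analysis and lists them separately. Such events are collected, because unsolicited AEs are recorded through V3.

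**Step 2. Length of the gap.** For a subject with V3 on day d, the uncounted days number d − 28, with d between 28 and 35.
- V3 on D28: 28 − 28 = 0 days.
- V3 on D35: 35 − 28 = 7 days, which is 7/36 = 19% of the calendar days D0 to D35.

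The documents give no distribution of V3 dates, so the range is 0 to 7 days per subject.

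**Step 3. Effect of one case on the reported row.** The formula is the Clopper-Pearson interval in SAP 2.5.8.3, with r events in n subjects and α = 0.05:
- lower limit = 1 − Beta(1 − α/2, n − r + 1, r), taken as 0 when r = 0
- upper limit = Beta(1 − α/2, r + 1, n − r)

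The planned group sizes are 55 per group in Cohort 2, and 55 + 5 = 60 per QIV-HD group when the cohorts are combined. QIV-SD stays at 55. As an illustration, assume one non-serious AESI with onset between D29 and V3.

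| n | Overview row as planned | Counted through V3 |
|---|---|---|
| 55 | 0/55 = 0% (0 to 6.49%) | 1/55 = 1.82% (0.05 to 9.72%) |
| 60 (QIV-HD, cohorts combined) | 0/60 = 0% (0 to 5.96%) | 1/60 = 1.67% (0.04 to 8.94%) |

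For r = 0 the upper limit reduces to 1 − 0.025^(1/n). With n = 55 this is 1 − 0.9351 = 6.49%, which agrees.

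**The case against.** The strongest reply is that no recorded AESI disappears. The AESI listing carries no stated 28-day limit, so a Table 7 event after D28 should appear there under its own category. Serious cases also reach the whole-study SAE tables by SOC, PT, seriousness, outcome and relatedness. With counts this small, a reader of the listing would find a single case. The events that reach no table must be AESIs, non-serious, with onset after D28, in a subject whose V3 is later than D28. The SAE definition includes important medical events and gives new-onset autoimmune disease as an example, so conditions of this type may often be reported as serious. All of this stands and limits the consequence. It does not remove the mismatch, because a listing is not the summary that the protocol specifies and the documents do not make every AESI serious.

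A reader might infer three stronger things that the documents do not support:

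- **That about a fifth of AESIs would be lost.** The 19% is a ceiling on days for a subject seen on D35. It is zero for a subject seen on D28, and a share of days is not a share of events.
- **That the analysis ignores the investigator's flag.** The SAP defines retrieval through Table 7 and is silent on the flag. It does not say that the flag is disregarded. Retrieval by coded term is a reproducible rule, and Table 7 adds related terms for several of the five named conditions. No PT for a protocol-named AESI has been identified that it would miss. What is lacking is a statement of how the two sources are reconciled.
- **That the SAE and death rows of the overview share the defect.** They share the 28-day heading, but SAEs already have whole-study tables and deaths have a listing.

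**Conclusion.** The plan is inconsistent on this point. The endpoint covers "relationship to vaccination of AESIs throughout the study (D0 through V3"), the protocol plans a whole-study summary, and the SAP provides a 28-day count plus a listing without declaring a change. This is a stated window that contradicts the endpoint, not merely detail left unwritten.

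The consequence is minor. The gap is 0 to 7 days per subject and affects only subjects whose V3 is after D28. One case would turn 0/55 (upper limit 6.5%) into 1/55 (1.8%; 0.05 to 9.7%) in the AESI row. That illustration assumes a single non-serious event in the gap and the planned group sizes. The documents give no AESI rate, and the expectation that such events are very rare is an assumption. The missing breakdown by SOC, PT and relationship does not depend on any event falling in the gap.

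**What to change.** Add one AESI table to SAP 2.4.4.1, covering D0 through V3, by SOC and PT, for all and related events, as protocol 12.1.1.2 states. Keep the 28-day AESI row in the overview and add a footnote pointing to the new table. Leave the SAE and death rows as they are.

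As a secondary clarification, state in SAP 2.5.2.4 how the investigator's AESI flag is reconciled with Table 7 retrieval, for example by listing events that are flagged but outside Table 7, or in Table 7 but not flagged.

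The cost is a few lines of SAP text, one small table and possibly one short listing, all from data already collected. The AESI table would cover a slightly longer period than the overview, which the footnote explains.

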### ***Solicited reactions***

The following solicited reaction summaries will be presented using the terms prelisted in CRB.

- Summary of solicited reactions (Solicited injection site reactions and Solicited systemic reactions) within 7 days after vaccine injection by intensity (Grade 2, Grade 3, and Grade 2 or 3)
- Solicited injection site reactions (injection site pain, injection site erythema, injection site swelling, injection site induration, and injection site bruising) and solicited systemic reactions (fever, headache, malaise, myalgia, and shivering) within 7 days after vaccine injection:
  - By maximum intensity
  - By time of onset
  - By number of days of occurrence during the solicited period
  - By overall number of days of occurrence

Listings of solicited reactions (solicited injection site reactions and solicited systemic reactions) will be presented. Action taken and whether the reaction led to early termination from the study will be displayed in the listings. Solicited reactions not included in the safety analysis will be also presented in listings.

### ***Unsolicited non-serious AEs***

- Summary of unsolicited non-serious AEs and ARs within 28 days after vaccine injection
  - By maximum intensity (Grade 1, Grade 2, Grade 3, and Missing)
  - By time of onset
  - By duration
- Unsolicited AEs and ARs within 28 days after vaccine injection by SOC and PT
- All and related AEs leading to study discontinuation within 28 days after vaccine injection

Listings of unsolicited non-serious AEs will be presented. Unsolicited non-serious AEs not included in the safety analysis will be also presented in listings.

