### **Unsolicited AE/AR:**

An unsolicited AE is an observed AE that does not fulfill the conditions prelisted in the CRB in terms of symptom and/or onset post-vaccination, i.e., excluding solicited reactions, e.g., if headache between D0 and D7 is a solicited reaction (i.e., prelisted in the CRB), then a headache starting on D7 is a solicited reaction, whereas headache starting on D8 post-vaccination is an unsolicited AE. Unsolicited AEs includes both serious (SAEs) and non-serious unsolicited AEs.

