**Intensity:**

The intensity for SAE will be computed using the same methodology than for unsolicited non-serious AEs described in [Section 2.5.2.2](#).

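### The SAP's itemised summaries of unsolicited AEs by maximum intensity, onset and duration cover non-serious events only, although the protocol plans them for all unsolicited AEs

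*SAP*

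**What the plan says.** Protocol 12.1.1.2 describes the unsolicited-AE summary as "Unsolicited AEs occurring within 28 days after the day of injection by system organ class (SOC) and PT, time to onset, duration, maximum intensity", followed by relationship to vaccination. It does not restrict this to non-serious events. A separate item covers SAEs: "All SAEs that occur throughout the study by SOC and PT, time to onset, seriousness criteria, outcome and relationship to vaccination". The SAP's own SAE endpoint (SAP 2.1.4) also names onset: "Occurrence, nature (MedDRA PT), time to onset, seriousness criteria, relationship to vaccination, outcome".

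The definition is the same in Protocol 9.1.1 and SAP 2.1.4.1.1: "Unsolicited AEs includes both serious (SAEs) and non-serious unsolicited AEs".

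In SAP 2.4.4.1, under the heading for unsolicited non-serious AEs, the breakdowns by maximum intensity, time of onset and duration hang on one item: "Summary of unsolicited non-serious AEs and ARs within 28 days after vaccine injection". The next item drops the restriction but has no such breakdown: "Unsolicited AEs and ARs within 28 days after vaccine injection by SOC and PT". The Generalities of the same section say: "Unsolicited AEs will also be tabulated by relationship to the vaccine group and intensity".

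The SAE outputs in SAP 2.4.4.1 are counts within 7 days, within 28 days and over the whole study, then tables by seriousness criterion, SOC and PT, and outcome, plus listings. SAP 2.5.2.3 nevertheless derives SAE onset, duration and intensity; on the last it says: "The intensity for SAE will be computed using the same methodology than for unsolicited non-serious AEs". SAP 1.6 reports no statistical modification.

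**The concern.** Describing safety is one of the study's two objectives, and the protocol says how unsolicited AEs are to be described. By its terms that description includes SAEs. A programmer who works from the SAP's itemised list would produce intensity, onset and duration tables without them. Anyone comparing those tables with the protocol would have no declared change to explain the gap.

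The restriction also works in one direction for the most severe category. Removing serious events from a Grade 3 count cannot raise it. At stake is whether the reported Grade 3 frequency of unsolicited AEs is the one that the protocol defines. The completeness of SAE reporting as such is not in question.

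**Working it through.** The plan states no figure on this point, so the check compares planned outputs attribute by attribute and then gives one illustration of scale.

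| Attribute | Protocol 12.1.1.2: unsolicited AEs (SAEs included) | Protocol 12.1.1.2: SAE item | SAP 2.4.4.1: non-serious AEs | SAP 2.4.4.1: SAEs |
|---|---|---|---|---|
| SOC and PT | planned | planned | one table for all unsolicited AEs | table |
| Maximum intensity | planned | not named | table | no itemised table; general rule only |
| Time to onset | planned | planned | table by category | cumulative windows only |
| Duration | planned | not named | table | no itemised table |

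**Intensity.** The general rule in SAP 2.4.4.1 covers SAEs through the SAP's own definition, while the itemised table does not. The two statements conflict.

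**Duration.** The itemised table is for non-serious events only, and the general rule does not mention duration. SAP 2.5.2.3 derives SAE duration with no itemised table to use it.

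**Onset.** SAP 2.5.2.2 sets categories for non-serious events: D0-D3, D4-D7, D8-D14, D15 or later, and missing. SAEs get no such table. Their onset shows only through the cumulative windows, and the two SAP sections disagree on these: 2.4.4.1 lists 7 days, 28 days and the whole study, whereas 2.5.2.3 lists only the last two.

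**Data.** Protocol 9.1.3.3 records intensity and start and stop dates for every unsolicited AE, serious or not. The inputs will therefore exist.

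**Direction.** With the same denominator, subjects with a Grade 3 non-serious unsolicited AE are a subset of subjects with any Grade 3 unsolicited AE. The Grade 3 count in the non-serious table is thus equal to or below the count under the protocol's description.

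**Scale.** Inputs: n = 55 per Cohort 2 arm (SAP 1.3) and the Clopper-Pearson interval of SAP 2.5.8.3. Assumption, not from the documents: one subject in an arm has a Grade 3 SAE with onset within 28 days, and this is the only unsolicited event in that arm of at least Grade 3 and the only one in that subject.

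- Non-serious only, r = 0: 0/55. The lower limit is 0. The upper limit is 1 − 0.025^(1/55) = 0.0649, or 6.5%.
- All unsolicited AEs, r = 1: 1/55 = 1.8%. The lower limit is 1 − 0.975^(1/55) = 0.0005, or 0.05%. The upper limit is the 97.5th percentile of Beta(2, 54) = 0.0972, or 9.7%.

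In a QIV-HD arm pooled over both cohorts (55 + 5 = 60), the same subject is 1/60 = 1.7%.

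**The case against.** The strongest reply is that the SAP already covers SAEs by other routes. The general rule commits to an intensity tabulation of unsolicited AEs. The safety overview has separate rows for all unsolicited AEs, non-serious AEs and SAEs. The SOC and PT table includes SAEs. SAEs also have their own tables, listings are planned, and deaths are listed. The intensity table is labelled non-serious, so 0/55 would be correct for what it claims to show, and the same subject would be counted among the SAEs. The protocol's SAE item names neither intensity nor duration, so the SAP may be read as giving each class of event its own attributes. The protocol also does not prescribe onset categories.

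Much of this stands, and it rules out three stronger readings:

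- A reader might infer that SAEs are absent from any severity tabulation. The general rule in SAP 2.4.4.1 does not allow that; the fault is a conflict between that rule and the itemised list.
- A reader might infer that SAE onset is never tabulated. The cumulative windows are a tabulation of onset, though a coarse one.
- A reader might infer that the most severe events are the ones left out. Protocol 9.1.1 and SAP 2.1.4.1.1 separate serious from severe: an SAE can be of any grade, and Grade 3 non-serious events remain in the table.

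What the reply does not answer is the protocol's unsolicited-AE item, which includes SAEs by definition and asks for all three attributes. The general rule is silent on onset and duration. The SAP does not specify the columns of the SAE listing, so the listing cannot be counted on to supply grade or onset.

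**Conclusion.** Wrong as written, and minor. The itemised summaries by maximum intensity, onset and duration are narrower than Protocol 12.1.1.2 plans, and on intensity they contradict the SAP's general rule. The departure is not declared. SAE onset is reported only in cumulative windows that differ between two SAP sections, and the derived SAE duration and intensity have no itemised table.

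The effect on the Grade 3 row is either nothing or an understatement. In the illustration it is one subject, 0% against 1.8% of an arm. That rests on the assumed Grade 3 SAE; the documents give no expected SAE rate, and an arm without SAEs is unaffected. The study is descriptive with no hypothesis tests, so no formal conclusion changes. The documents do not support the reading that SAEs would go unreported.

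**What to change.** In SAP 2.4.4.1:

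- Run the summaries by maximum intensity, time of onset and duration on all unsolicited AEs and ARs, serious and non-serious. Keep a non-serious version alongside if it is wanted.
- Under the SAE outputs, add a table by time of onset with the categories of SAP 2.5.2.2, or state that the SAE listing shows onset and grade.
- Make the SAE periods the same here and in SAP 2.5.2.3.

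If the sponsor prefers to keep the restriction, declare it in SAP 1.6 as a departure from Protocol 12.1.1.2 and reword the general rule on intensity to match.

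The cost is SAP wording and a few table shells. The variables are already derived in SAP 2.5.2.3, and no new data are needed.
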